11.7.3 Physical Examinations and Vital Signs

A PE of all body systems and vital signs assessment will be performed at screening and select study visits (see [Table 3-1](#) and [Table 3-2](#)). At other visits, symptom-directed PEs and symptom-directed vital sign assessments can be performed at the discretion of the investigator or healthcare provider.

A PE includes a review of the following systems: head/neck/thyroid, eyes/ears/nose/throat (EENT), respiratory, cardiovascular, lymph nodes, abdomen, skin, musculoskeletal, and neurological. Breast, anorectal, and genital examinations will be performed when medically indicated. After screening, any clinically significant abnormal findings in PEs will be reported as AEs.

Vital signs include blood pressure (systolic and diastolic), oral temperature, pulse rate, and respiration rate. These will be assessed following a 5-minute rest in the seated or supine position.

11.7.4 Electrocardiograms

Standard 12-lead ECGs will be performed using a machine with printout according to the Schedule of Assessments ([Table 3-1](#) and [Table 3-2](#)). A window of ± 15 minutes will be allowed around the nominal times for all postdose ECG assessments. Additional standard 12-lead ECGs will be performed at any other time if clinically indicated.

The performance of all ECGs will adhere to the following guidelines:

- The subject will be instructed to rest in the supine position for at least 5 minutes before having an ECG performed.
- The ECG will be performed before any other procedures that may affect heart rate (HR), such as blood draws.

The ECG traces will be manually read at the study site at the Screening and Safety Follow-up Visits. A printout of the ECG traces will be made for safety review by the investigator and maintained with source documentation. Clinically significant ECG abnormalities occurring during the study through the Safety Follow-up Visit will be recorded as AEs.

To ensure safety of the subjects, a qualified individual at the study site will make comparisons to baseline measurements. If the QTcF is increased by >45 msec from the baseline or an absolute QTcF value is ≥ 500 msec for any scheduled ECG, 2 additional ECGs will be performed approximately 2 to 4 minutes apart to confirm the original measurement. If

either of the QTcF values from these repeated ECGs remains above the threshold value (>45 msec from baseline or ≥ 500 msec), a single ECG will be repeated at least hourly until QTcF values from 2 successive ECGs fall below the threshold value that triggered the repeat measurement.

If the QTcF value remains above the threshold value (>45 msec from the average of the 3 predose values on Day 1 or ≥ 500 msec) on repeated measurement or is noted on >2 occasions with no identified alternative etiology for the increased QTcF study drug, then discontinuation from study drug treatment may be required after discussion with the Medical Monitor.

Subjects who discontinue study drug treatment for increased QTc should have their QTc monitored closely until it normalizes or returns to baseline.

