demographics, background, and baseline characteristics and also to efficacy data analyses, including the primary endpoint analysis. In addition, *period baseline* is defined as the most recent non-missing measurement (scheduled or unscheduled) collected before the first dose of study drug in each Treatment Period. For Treatment Period 2, the baseline should be from an assessment measured after the TE period for Treatment Period 1. This definition will be applied to all safety data analysis. For ECG, baseline for Period 1 will be defined as the average of the 3 pretreatment measurements on Day 1. For sweat chloride, the study baseline value will be the mean of assessment values on the left and the right arm at the most recent time point prior to the first dose of study drug in the study. If the result from only one of the arms is available then the result from that arm will be considered as baseline.

**Change (Absolute change) from study baseline** will be calculated as post-baseline value – study baseline value.

**Relative change from study baseline** will be calculated as  $100 \times (\text{post-baseline value} - \text{study baseline value}) / \text{study baseline value}$ .

**Change (Absolute change) from period baseline** will be calculated as post-baseline value – period baseline value.

**Relative change from period baseline** will be calculated as  $100 \times (\text{post-baseline value} - \text{period baseline value}) / \text{period baseline value}$ .

**Unscheduled Visits:** Unscheduled visit measurements will be included in the following:

- (1) derivations of measurements at scheduled visits per specified visit windowing rules below;
- (2) derivations of baseline/last on-treatment measurements;
- (3) derivations of the maximum/minimum on-treatment values and maximum/minimum changes from baseline values for safety analyses;
- (4) data listings where appropriate.

**Visit Windowing Rules:** Section 10.2 defines the windows for protocol-defined visits. The windows will be applied using the following rules for both scheduled and unscheduled visits:

- (1) If no measurement is available within a visit window, the assessment will be considered missing for the visit;
- (2) If there is more than one measurement available within the same visit window, use the following rules:

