  - For all efficacy parameters, if there are multiple measurements within a visit window, the record at the scheduled visit will be used. If there are no measurements at the scheduled visit:
    - the record closest to the target day will be used.
    - If there are multiple records with the same distance to the target day, the latest record will be used.
    - Assessments at early treatment termination (ETT) visit will follow the windowing rules for regular visits up to Week 24.

- A safety follow-up visit (SFUV) assessment will follow the windowing rules for regular visits if it falls within the upper boundary of the visit window for Week 8 (period 1) or Week 24 (period 2), or remain as SFUV otherwise.
- For all safety parameters, if there are multiple measurements within a visit window, then 1) the record closest to the target day will be used; 2) if there are multiple records within the same distance from the target day, the latest record will be used; 3) SFUV will not be windowed, instead, used per nominal visit in relevant analyses.

Note: spirometry assessments, BMI, weight, and height will be used for both efficacy and safety purposes. The corresponding measurements will follow visit windowing rules for efficacy.

**Incomplete/Missing data** will not be imputed, unless otherwise specified.

**Outliers:** No formal statistical analyses will be performed to detect or remedy the presence of statistical outliers, unless otherwise specified.

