### **8.4.3 Standard 12-Lead Electrocardiogram**

For treatment-emergent ECG measurements, a summary of raw values and change from period baseline values will be provided by treatment group at each scheduled time point for the following standard 12-lead ECG measurements: PR, QTc for HR intervals (QTcF), QRS duration, and HR. In addition, the mean value at each time point will be plotted by treatment group for QTcF and heart rate.

The number and percentage of subjects with ECG measurements meeting the threshold analysis criteria during the visit window for analysis visits will be summarized by analysis visit. Similarly, the ECG measurements meeting the threshold analysis criteria during the

overall TE period will be presented. The threshold analysis criteria are provided in Section 10.5 (Table 10-9).

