## Note:

1. For spirometry and ECG data on Day 1 and Day 15 of each treatment period, no visit windowing rule shall be applied. Instead, nominal visit will be used.
2. On Day 1 of period 1, the pre-dose ECG measurements are collected as triplicates. The average of pre-dose triplicates will be used as baseline. Only the pre-dose assessments of the triplicate will be used for the baseline. If all the measurements for triplicates are missing or post-dose, the last non-missing pre-dose assessment will be used as the baseline.
3. For all efficacy parameters, if there are multiple measurements within a visit window, the record at the scheduled visit will be used.
  - If there are no measurements at the scheduled visit, then the record closest to the target day will be used
  - If there are multiple records with the same distance to the target day, the latest record will be used.
  - Assessments at early treatment termination (ETT) visit will follow the windowing rules for regular visits up to Week 24.
  - A safety follow-up visit (SFUV) assessment will follow the windowing rules for regular visits if it falls within the upper boundary of the visit window for Week 8 (period 1) or Week 24 (period 2), or remain as SFUV otherwise.
4. For all safety parameters:
  - If there are multiple measurements within a visit window, then the record closest to the target day will be used
  - If there are multiple records with the same distance to the target day, the latest record will be used.
5. Spirometry, BMI, Weight and Height will follow the efficacy windowing rules.

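### At Weeks 4, 8, 20 and 24 the SAP's windowing rule replaces a QTcF that triggered repeat ECGs with the last same-day repeat, so the by-visit QTcF summaries and mean plot are biased slightly downward

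*Protocol*

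**What the plan says.** **Protocol 11.7.4.** The trigger reads "If the QTcF is increased by >45 msec from the baseline or an absolute QTcF value is" 500 msec or higher, on any scheduled ECG. Then "2 additional ECGs will be performed approximately 2 to 4 minutes apart to confirm the original measurement". If either of these is still above the limit, "a single ECG will be repeated at least hourly until QTcF values from 2 successive ECGs fall below the threshold value" that set off the series.

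**SAP 8.1.** Unscheduled measurements enter the "derivations of measurements at scheduled visits per specified visit windowing rules below". They also enter the "derivations of the maximum/minimum on-treatment values and maximum/minimum changes from baseline values for safety analyses", and the listings. For safety parameters with several records in a window, the record closest to the target day is used. On a tie, "if there are multiple records within the same distance from the target day, the latest record will be used". The scheduled record has no priority. For efficacy parameters it does.

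**SAP 8.4.3.** For ECG parameters "a summary of raw values and change from period baseline values will be provided by treatment group at each scheduled time point", with a plot of mean QTcF. The same section plans counts of subjects meeting the Table 10-9 criteria, by visit window and over the whole treatment-emergent (TE) period.

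**SAP 10.2, Note 1.** "For spirometry and ECG data on Day 1 and Day 15 of each treatment period, no visit windowing rule shall be applied"; the nominal visit is used instead. Weeks 20 and 24 map to the analysis visits Week 4 and Week 8.

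**The concern.** Each rule is reasonable alone. Together they choose the visit value by its size: only high readings are measured again, the series stops once readings are low, and the SAP keeps the last one. Low readings caused by noise are never measured again. The replacement goes one way and happens more often on a treatment that prolongs QTcF, so it pulls the active-versus-placebo contrast toward no difference.

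Protocol 9.4 says the combination's QT effect has not been evaluated in a thorough QT study. SAP 8.4 plans only descriptive safety analysis. In the visible text, these summaries and the plot are the only planned average QTcF comparison at Weeks 4 and 8. Because Day 1 and Day 15 keep the nominal ECG, one table and plot also mixes two selection rules, and a small part of any fall from Day 15 to Week 4 could come from the rule itself.

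**Working it through.** The plan gives no figure to reproduce. The check has two parts.

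**1. Following one triggered ECG through the rules**

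- If both confirmatory repeats are below the limit, the last record is below it. Otherwise the series runs until two in a row are below, and again the last record is below. A completed series therefore ends under the threshold that triggered it.
- SAP 8.1 admits the repeats to the visit derivation.
- The ECG windows in SAP 10.2 are in days (targets Day 29 and Day 57), so same-day records tie and the latest is taken. At least two repeats follow any trigger, so the triggering record is never the latest.
- The selected value feeds the raw and change summaries, including the maximum, and the mean plot.
- The threshold tables refer to measurements within the window or period. With the same baseline, a rise above 45 msec also meets the Table 10-9 criterion of more than 40 ms, and 500 ms or more has its own line. The exceedance is counted.

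A simulation of the repeat rule agrees (assumed baseline 410 msec, SD 18; visit shift 15, SD 20; replicate SD 8; shift decaying 3% per hourly repeat). With same-day completion, the selected value was above the trigger in 0 of 32,783 triggered visits, and all 32,783 met a threshold criterion on some record. With the series cut after six hourly repeats, 8,382 of 33,172 selected values (25%) were still above the trigger.

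**2. Size of the bias in the mean**

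Assumptions, none from the documents except the counts and the triplicate baseline:

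- subjects per treatment: 204 × 2 periods / 3 treatments = 136
- SD of true change: 8 msec
- single-ECG SD σ: 8 to 12 msec
- triplicate Day 1 baseline; only the 45 msec trigger is modelled

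SD of the observed change = √(8² + σ²(1 + 1/3)):

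- σ = 8: √(64 + 85.3) = 12.22
- σ = 12: √(64 + 192) = 16.0

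Expected triggers per visit = 136 × [1 − Φ((45 − true mean)/SD)]. Bias = (triggers/136) × (mean triggering value − mean after replacement). Both means come from simulating the repeat rule, 400,000 subjects per setting.

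| True mean change | σ | Triggers of 136 | Triggering mean | After replacement | Bias (msec) |
|---|---|---|---|---|---|
| 0 | 12 | 0.33 | 49.9 | 20.8 | 0.07 |
| 10 | 8 | 0.28 | 48.7 | 30.7 | 0.04 |
| 10 | 12 | 1.95 | 50.6 | 25.2 | 0.36 |
| 20 | 8 | 2.77 | 49.5 | 33.9 | 0.3 |
| 20 | 12 | 8.04 | 51.9 | 29.3 | 1.3 |

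Example, third row: 1 − Φ(35/16) = 0.0144; × 136 = 1.95; 1.95/136 × (50.6 − 25.2) = 0.36. The bias is a difference between two records of the same subject, so it does not depend on which baseline is subtracted.

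**The case against.** **The exceedances are still reported.** This stands. Both threshold tables, the maximum on-treatment derivations and the individual listings keep them, and clinically significant ECG abnormalities are recorded as adverse events. A reader might infer that all by-visit ECG tables lose every triggering QTcF. SAP 8.4.3 does not support that.

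**The by-visit value can still be high.** This also stands. A reader might infer that no Week 4 or Week 8 value can ever show an exceedance. There are three exceptions:

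- A series that runs past midnight, where the closest-day rule can leave a value above the trigger.
- A series triggered at 500 msec or more, which may stop below 500 and still be over 45 msec above baseline.
- Period 2, where the SAP change uses the period baseline but Protocol 11.7.4 refers to the average of the Day 1 predose values.

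**Most of the drop is regression to the mean.** This is true. At a true change of 10, a single unselected repeat would average 10 + (85.3/149.3) × 38.7 = 32.1 for σ = 8, and 10 + (112/256) × 40.6 = 27.8 for σ = 12. Those are close to the 30.7 and 25.2 above. It does not remove the bias. The scheduled readings of all subjects average correctly, and re-measuring only the high ones does not.

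**The affected visits carry the least ECG information, and no test is planned.** This is fair. Serial postdose ECGs occur only at Weeks 1, 2, 17 and 18, which Note 1 protects. It lowers the priority and does not justify the rule.

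**Postdose tracings.** A reader might infer that a postdose repeat would be filed as a predose value. No dose is given at Weeks 8 and 24, and nothing says whether a subject in an hourly series at Week 4 or 20 is dosed. That cannot be claimed.

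**Conclusion.** The interaction is real and of minor severity. At Weeks 4, 8, 20 and 24 the by-visit raw and change-from-period-baseline QTcF summaries and the mean plot use a value selected downward, and the by-visit maximum generally omits the reading that triggered the repeats. Under the assumed SDs the mean is understated by 0.04 to 0.36 msec at a true 10 msec effect, 0.3 to 1.3 msec at 20 msec, and at most 0.07 msec with no effect. At 20 msec, at least 20 − 1.3 = 18.7 msec remains visible. The documents do not support saying that a QT signal would be hidden.

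The direction of the bias follows from the rules alone, and its size rests on the assumed SDs. The conclusion also assumes that the repeats are entered in the analysis data and usually finish on the day of the visit. The available text of SAP 10.2 begins part-way through its window table, so an introductory line about repeat records could not be checked.

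**What to change.** In SAP 8.1 and 10.2:

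- For by-visit ECG summaries and plots at Weeks 4, 8, 20 and 24, use the nominal scheduled ECG, as Note 1 does for Day 1 and Day 15 and as the efficacy rule does. If there is no scheduled record, use the closest day and the first record on that day.
- State that the threshold tables, maximum on-treatment derivations and listings use all records, including the Protocol 11.7.4 repeats. SAP 8.1 names maxima and listings as uses of unscheduled records but does not name the threshold tables.

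The cost is a short SAP edit and a small programming change before database lock, with no new data. The protocol's repeat-ECG procedure is unchanged.

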11.7.5 Contraception and Pregnancy

11.7.5.1 Contraception

The effects of VX-661 monotherapy or in combination with ivacaftor on conception, pregnancy, and lactation in humans are not known. Neither VX-661 nor ivacaftor showed any genotoxic potential in a standard battery of in vitro (Ames test, Chinese hamster ovary cell chromosomal aberration) and in vivo (mouse micronucleus) studies. VX-661 and ivacaftor were each found to be nonteratogenic in reproductive toxicology studies in rats and rabbits.^{27,28} Subjects should follow the contraception requirements outlined in this study protocol. The effects of VX-661 monotherapy or in combination with ivacaftor on the PK of hormonal contraceptives are not known. Thus, hormonal contraception is not an acceptable method of contraception for female subjects though it is acceptable for the female partners of male subjects.

At this stage in the development of VX-661 in combination with ivacaftor, participation in this study requires a commitment from the research subject and his/her partner to use at least 1 effective method of birth control. Acceptable methods of contraception for participants of this study and their partners are listed below. Methods of contraception should be in successful use from signing of consent, approximately 28 days, before the first dose of study drug (unless otherwise noted) and until 90 days following the last dose of study drug.

Contraception for the couple is waived for the following:

- True abstinence for the subject, when this is in line with the preferred and usual lifestyle of the subject. Periodic abstinence (e.g., calendar, ovulation, symptothermal, and postovulation methods) and withdrawal are not acceptable methods of contraception.
- If the male is infertile (e.g., bilateral orchiectomy). Infertility may be documented through examination of a semen specimen or by demonstration of the absence of the vas deferens by ultrasound or medical record before the first dose of the study drug.
- If the female is of non-childbearing potential, per the following:
 - o Postmenopausal: spontaneous amenorrhea for at least 12 consecutive months and serum FSH level ≥ 40 mIU/mL at Screening
 - o Documented hysterectomy or a bilateral oophorectomy/salpingo-oophorectomy

- o Has not achieved menarche (has not had her first menstrual period). Females who fall into this category are considered not to be of childbearing potential only as long as they have not had their first menstrual period. If a female achieves menarche during the study, she will need to provide consent for compliance (proper method of contraception or abstinence).
- NOTE: All other female subjects who have had their first menstrual period will be considered to be of childbearing potential.

Acceptable contraceptive methods:

Acceptable contraceptive methods for **male subjects** or **male partners** of female subjects include the following:

- Vasectomy 6 months or more previously, with a documented negative postvasectomy semen analysis for sperm.
- Condom and spermicide.
 - o In countries where spermicide is not available, condom without spermicide will be considered acceptable.
 - o Local regulations may require use of an additional acceptable method of contraception.

Acceptable contraceptive methods for **female subjects** include the following:

- Bilateral tubal ligation performed at least 6 months previously.
- Continuous use of an intrauterine device (non-hormone-releasing) for at least 90 days before the first dose of study drug.
- Barrier contraception (such as diaphragm, cervical cap, or female condom) and spermicide.
 - o In countries where spermicide is not available, barrier contraception without spermicide will be considered acceptable.
 - o Local regulations may require use of an additional acceptable method of contraception.
- NOTE: Hormonal contraceptives will not be considered as an effective method; however, female subjects are not required to discontinue hormonal contraceptives.

Acceptable contraceptive methods for **female partners** of male subjects:

- Bilateral tubal ligation performed at least 6 months previously.
- Continuous use of an intrauterine device for at least 90 days before first dose of study drug.
- Barrier contraception (such as diaphragm, cervical cap, or female condom) and spermicide.

- o In countries where spermicide is not available, condom without spermicide will be considered acceptable.
- o Local regulations may require use of an additional acceptable method of contraception.
- Hormonal contraceptives, if successfully used for at least 60 days before first dose of study drug.

Additional notes:

- Acceptable methods of contraception listed above are examples. Local requirements may prohibit the use of some of these examples. Please contact the Medical Monitor with any questions.
- A female condom cannot be used with a male condom (as a double method of contraception) due to risk of tearing.
- Male and female subjects who are not sexually active at the time of screening must agree to follow the contraceptive requirements of this study if they become sexually active with a partner of the opposite sex.
- If applicable, additional contraception requirements may need to be followed according to local regulations and/or requirements.
- Male subjects must not donate sperm after the first dose of study drug, throughout the study, and for 90 days following the last dose of study drug.
- Female subjects and female partners of male subjects should not plan to become pregnant during the study through 90 days following the last dose of study drug.
- Male subjects whose female partner becomes pregnant through well-documented in vitro fertilization (donated sperm) or banked sperm (collected before the subject received study drug) must be compliant with the contraception requirements. In this scenario, the male subject and his female partner must commit to using barrier methods of contraception (to ensure there is no exposure of the fetus to study drug) for the duration of the study and until 90 days after the last dose of study drug.
- Female subjects should not nurse a child from the start of study drug dosing through 90 days following the last dose of study drug.
- Unique situations that may not fall within the above specifications should be discussed with the Medical Monitor.

